### Dispensing Visit (Pair 2)

- The subject will undergo a saline washout.
- The second study pair of contact lenses will be selected by the investigator according to the randomization table [REDACTED] for insertion by the subjects. Subjects will be dispensed the lens power nearest to their refractive error requirement.
- Lenses should be allowed to settle for 10 minutes.
- An initial fit assessment will be made to ensure lens fit is acceptable (Y/N). The subject should be discontinued and exited if the lens fit is found unacceptable and the primary reason for poor fit recorded on the CRF and video footage of the fit collected.
- Monocular spherical over-refraction (SOR) will be conducted to determine if a different lens power is required.
- Monocular and binocular **HIHC** and **HILC** distance logMAR visual acuities will be recorded (SOR will be used if the subject is wearing monovision).
- Final lenses will be inserted and allowed to settle for a further 10 minutes, if applicable.
- Subjective responses will be collected per the Post-Settling Questionnaire [REDACTED], including:
  - [REDACTED]
  - [REDACTED]
  - [REDACTED]
  - [REDACTED]
  - [REDACTED]
  - [REDACTED]
  - [REDACTED]
  - [REDACTED]
  - Lens movement/awareness (5-point Likert scales)
  - Vision (7-point Likert & 100-point scales)
- Lens surface will then be assessed and graded after settling per guidelines detailed in the CVI grading scales [REDACTED]
  - [REDACTED]
  - Wettability (0-4 scale)
  - [REDACTED]
  - [REDACTED]

- Lens fit will then be assessed and graded according to the guidelines detailed in CVI Grading scales ( [REDACTED] ).
  - Lens centration (0.1mm steps)
  - [REDACTED]
  - Post-blink movement (0.1mm steps)
  - Mobility rating (0.50 steps)
  - Overall lens movement (-2 to +2 scale)
  - Overall lens fit acceptance and investigator reason, if unacceptable (0.25 steps).  
Video will be recorded in the event of poor fit.
- The subject will be instructed to wear the study lenses for a minimum of 8 hours per day / 6 days per week.
- The subject will be dispensed adequate lenses (including spares) to last them until the next study visit.
- The subject will be discharged and scheduled to return for Visit 3 within the required study visit window.

#### 7.3.4 Visit 3: Two-Week Follow-up on Pair 2 (-1/+4 days) & Exit

*Subjects will be asked to wear lenses for at least 3 hours prior to the visit appointment.*

- Subjective response will be collected per the Final Questionnaire [REDACTED] including:
  - Overall satisfaction (7-point Likert scale)
  - Comfort satisfaction & comfort rating (7-point Likert & 100-point scales)
  - Comfort on insertion (7-point Likert & 100-point scales)
  - Comfort at end of day (7-point Likert & 100-point scales)
  - [REDACTED]
  - [REDACTED] s)
  - [REDACTED]
  - [REDACTED]
  - [REDACTED]
  - Lens handling (7-point Likert & 100-point scales)
  - [REDACTED]
  - [REDACTED]
  - Lens holding/handling (5-point Likert scales)
  - Vision (7-point Likert & 100-point scales)
- The following information will be collected from the subject by the investigator:

[figure not shown]

- Wear time at visit (hours).
  - Average time of insertion and removal during previous week, i.e. average time (hours).
  - Maximum wear time during previous week (hours).
  - Average time of day lenses become uncomfortable, if at all, i.e. average comfortable wear time (hours).
  - Use and frequency of comfort / re-wetting drops during past week (if any).
- Monocular and binocular **HIHC** and **HILC** distance logMAR visual acuities will be recorded (a spherical over-refraction will be performed for the distance eye and recorded first if the subject is wearing monovision).
  - Lens surface will then be assessed and graded after settling per guidelines detailed in the CVI grading scales (Appendix 4).
    - [REDACTED]
    - Wettability (0-4 scale)
    - [REDACTED]
    - [REDACTED]
  - Lens fit will then be assessed and graded according to the guidelines detailed in CVI Grading scales [REDACTED]
    - Lens centration (0.1mm steps)
    - Corneal coverage (Yes / No / Borderline)
    - [REDACTED]
    - Mobility rating (0.50 steps)
    - Overall lens movement (-2 to +2 scale)
    - Overall lens fit acceptance and investigator reason, if unacceptable (0.25 steps). Video will be recorded in the event of poor fit.
  - The lenses will be removed and stored in either an unbuffered or phosphate buffered (not borate) saline for return to the Sponsor.
  - Slit lamp biomicroscopy will be assessed according to the CVI approved study biomicroscopy CRF [REDACTED]
  - Subjective response will be collected per the Lens Preference Questionnaire [REDACTED]
  - Exit HIHC monocular distance logMAR visual acuities will be recorded with baseline spherocylindrical refraction in place (OD/OS).
  - The subject will be discharged and will sign the exit statement.

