## 2 Study Objective

---

This is a feasibility study to evaluate the clinical performance of a new silicone hydrogel formulation lens (Orion) in comparison with Gemini A ██████ over a period of two weeks of wear.

The primary variables of interest are:

- Vision

The secondary variables of interest are:

- Comfort/comfort preference
- Surface wettability performance
- Lens fit
- Lens handling
- Anterior ocular health

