### 2.1 Study Hypothesis

---

The primary hypothesis is that there will be no difference in vision performance between the Orion Test lens and the Gemini Control lens.

The secondary hypothesis is that there will be no difference in performance between the Orion Test lens and the Gemini Control lens for any of the secondary variables.

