## 10.2 Statistical analysis

---

Summary statistics will be produced (e.g. mean, standard deviation). Paired t-test will be used to compare slit lamp biomicroscopy, lens fit and subjective scores between study lens types. Repeated Measures Analysis of Variance (ANOVA) or paired analysis will be used to compare the variables between study visits. The critical alpha level for statistical significance will be set at  $p \leq 0.05$ , with adjustment for multiple comparisons.

All participants who were evaluated will be used in the analysis. In the event of missing data, individual data points will be excluded in the analysis and not extrapolated from the collected data.

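### Section 10.2 offers only a paired t-test between lenses, which does not suit three-category corneal coverage and leaves comfort preference with no applicable test

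*Combined protocol and SAP*

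**What the plan says.** Section 10.2 is unredacted and short. Its between-lens method is: "Paired t-test will be used to compare slit lamp biomicroscopy, lens fit and subjective scores between study lens types". The only other inferential method concerns visits: "Repeated Measures Analysis of Variance (ANOVA) or paired analysis will be used to compare the variables between study visits". The descriptive statistics are given by example: "Summary statistics will be produced (e.g. mean, standard deviation". No method for categorical or single-response data is named.

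Two outcomes matter here.

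- **Corneal coverage.** Section 7.3.4 lists it among the lens fit gradings at Visit 3 as "Corneal coverage (Yes / No / Borderline". Lens fit is a secondary variable in section 2. An item is redacted in the fit lists of the other visits, so nothing is claimed about coverage there.
- **Comfort preference.** Section 2 lists "Comfort/comfort preference" first among the secondary variables. It is collected at the last visit: "Subjective response will be collected per the Lens Preference Questionnaire". Table 2 ticks that questionnaire at Visit 3 only.

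Section 2.1 hypothesises that "there will be no difference in performance between the Orion Test lens and the Gemini Control lens for any of the secondary variables", so both outcomes need a comparison of lenses.

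**The concern.** A paired t-test needs a number for each lens in each subject, with differences that have a meaning. Corneal coverage gives a category. To run the test someone must choose how far Borderline lies from Yes and from No, and the visible plan does not say. If the choice is made after the data are seen, the size and even the direction of the lens difference can follow from it.

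Preference has a different problem. Asked once, after both lenses have been worn, it gives one comparative answer per subject, with no Test value and Control value to subtract. It is the outcome in which the subject compares the lenses directly, yet the plan gives no test, no rule for subjects with no preference and no account of lens order.

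**Working it through.** **Plan's own figures.** There are none to reproduce. Tables 3 and 4 size the study on acuity and on a numeric comfort score. The documents give no expected rates for coverage or preference. All rates and counts below are assumptions, apart from the planned 60 or so completers. The coverage examples take one result per subject and lens.

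**1. Does the coverage result depend on the code?** Take 60 subjects: 10 Borderline on Test (Yes on Control), 4 No on Control (Yes on Test), the rest Yes on both. Code Yes = 1, No = 0, Borderline = b. The mean Test minus Control difference is [10(b - 1) + 4]/60.

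| b | mean difference | t (59 df) | p |
|---|---|---|---|
| 0.1 | -5/60 | -1.45 | 0.15 |
| 0.5 | -1/60 | -0.39 | 0.70 |
| 0.9 | +3/60 | +1.50 | 0.14 |

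The same answers favour Control or Test according to b. The signed-rank statistic does not move. Under all three codes the 10 Borderline differences are the smaller ones (mid-rank 5.5, sum 55) and the 4 No differences the larger (mid-rank 12.5, sum 50).

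**2. Is the t-test liberal?** Simulation with 60 subjects, 20,000 runs, equal lenses, the three codes above and two levels of within-subject dependence:

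- No Borderline above 1% and no No answers: rejection rate 0.0004 to 0.004 at nominal 0.05. In 30% to 55% of runs all differences were zero and the test was undefined.
- 5% No and 10% Borderline: 0.023 to 0.047.

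The rate never exceeded 0.05.

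**3. Which replacement keeps the signal in No?** Take 60 subjects: 6 No on Test, 3 Borderline on Control, each paired with Yes, the rest Yes on both.

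- t-test in severity order (0, 1, 2): mean (6 × 2 - 3 × 1)/60 = 0.15, p = 0.083.
- Exact McNemar, No versus the rest: 6 against 0, p = 2 × (1/2)^6 = 0.031.
- Exact signed-rank in severity order: the three 1-step differences have mid-rank 2 (sum 6) and the six 2-step differences mid-rank 6.5. Of 2^9 = 512 sign patterns, 8 give a sum of 6 or less, so p = 2 × 8/512 = 0.031.
- Exact McNemar, not Yes versus Yes: 6 against 3, p = 2 × (84 + 36 + 9 + 1)/512 = 0.508.

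Pooling Borderline with No loses the difference, so that dichotomy should not stand alone.

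**4. What could a preference test show?** Exact two-sided binomial test against 50%, alpha 0.05 before any multiplicity adjustment and without stratification. The critical count c is the smallest with 2 × P(X ≥ c) ≤ 0.05.

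| No preference | n | c | power at 65:35 | power at 70:30 |
|---|---|---|---|---|
| 0% | 60 | 39 | 0.56 | 0.84 |
| 20% | 48 | 32 | 0.47 | 0.75 |
| 40% | 36 | 25 | 0.36 | 0.61 |

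At an observed even split, Wilson 95% intervals are 37.7% to 62.3% (30 of 60) and 34.5% to 65.5% (18 of 36). The study can detect a strong preference but not a mild one.

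**The case against.** The strongest reply is that much of the relevant material is not shown. Appendix 4 holds the fit grading scales and may contain a coverage score. The Lens Preference Questionnaire is visible only as a title. The wording in 10.2 refers to scores, and a preference is not obviously a score. These points stand in part. A coverage score cannot be excluded, but a three-category item would still be better served by a categorical or ordinal test. Preference is best described as having no applicable test, not as assigned to the t-test. If the item is graded, a one-sample signed-rank test would fit, and 10.2 does not name that either. The phrase allowing an unspecified paired analysis is tied to comparisons between visits, and preference is asked at only one.

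It is also fair that the impact is small. Coverage is one item within one secondary variable of a feasibility study. Overall fit acceptance is graded separately, and subjects whose initial fit is unacceptable are exited.

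Three stronger readings are tempting and are not supported:

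- **That the t-test would hide an excess of No entirely.** Coding the answers in printed order (Yes 1, No 2, Borderline 3) makes the example in step 3 cancel exactly (6 × 1 = 3 × 2, p = 1.0). No document prescribes that code, and the counts were chosen to cancel.
- **That the coverage test gives false positives.** Step 2 shows the opposite.
- **That recency will bias preference.** Assuming 70% prefer whichever lens came second and a 36:24 order split, the expected Test share is 0.7 × 0.6 + 0.3 × 0.4 = 54%. Neither input is in the documents. With a balanced 30:30 order it is 0.7 × 0.5 + 0.3 × 0.5 = 50%. Stratifying by order is sound practice, but no bias is shown.

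**Conclusion.** The point holds, within limits. For corneal coverage the rule in 10.2 is wrong as written: on the visible text it sends an unscored three-category item to a test whose answer depends on an unstated code. For comfort preference the gap is an omission, and naming a test is a free improvement.

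The size is moderate to small: lost power and an arbitrary estimand for secondary outcomes, with no sign of inflated type I error and no effect on acuity. The conclusion rests on two assumptions that unseen pages could change: that no coverage score is fixed in Appendix 4, and that preference is one comparative answer per subject. The numerical examples show the mechanism only and do not predict this study's data.

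**What to change.** Amend section 10.2 before unmasking:

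1. Limit the paired t-test to graded numeric scores.
2. For corneal coverage, report counts and percentages of Yes, Borderline and No per lens. Compare lenses with a prespecified paired ordinal test in that severity order, such as the exact Wilcoxon signed-rank test, supported by exact McNemar on No versus the rest. Do not rely on not Yes versus Yes alone. State how the two eyes are combined, which 10.2 does not say.
3. For preference, use an exact test stratified by lens order (Prescott if no-preference answers are kept, Mainland-Gart if only stated preferences count). If the item is graded, use a signed-rank test against no preference, with order accounted for. Report the Test share with its 95% confidence interval and the number with no preference.
4. Say whether these tests fall under the clause "with adjustment for multiple comparisons", whose method is not named.

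The cost is a few sentences in the analysis plan, with no new data, visits or subjects.

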### 7.3.5 Email Link or SMS Text Based Comfort Throughout the Day Questionnaire

### 7.3.6 Training for Use of the Study Products

The study subject will be instructed by the investigator as to the proper handling, insertion and removal techniques, proper use of the lenses, and the proper accounting and disposal of the used lenses.

Training will be in accordance with the information provided in a separate Subject Instruction Guide. The Subject Instruction Guide will be provided to the subject at the time of initial lens dispensing.

### 7.3.7 Summary of Visits and Procedures

Table 2 summarizes the visits and procedures for the study.

**Table 2: Summary of Visits and Procedures**

	Visit 1a Screening / Baseline	Visit 1b Dispense Pair 1	Visit 2 2-week follow-up Pair 1 & Dispensing of Pair 2	Visit 3 2-week follow- up Pair 2 & Exit
Informed consent	✓	-	-	-
Meet inclusion/exclusion criteria	✓	-	-	-
History at baseline	✓	-	-	-
Demographics	✓	-	-	-
Wearing time	✓	-	✓	✓
HVID / palpebral aperture size	-	✓	-	-
Auto-refraction & keratometry	✓	-	-	-
Sphero-cylindrical refraction	✓	-	-	-
HIHC & HILC VAs with sphero-cylindrical refraction	✓	-	-	-
Slit lamp biomicroscopy	✓	✓*	✓	✓
Instillation of lens at office	-	✓	✓	-
Subjective assessments	-	✓	✓	✓
Lens surface assessments	-	✓	✓	✓
Lens fit assessments	-	✓	✓	✓
Spherical over-refraction (SOR)	-	✓	✓	-
HIHC & HILC Distance VAs (with CLs)	-	✓	✓	✓
Lens Preference Questionnaire	-	-	-	✓
Exit VAs	-	-	-	✓
Study Exit	-	-	-	✓

\* Not applicable if Visit 1b occurs on the same day as Visit 1a

## 8 Adverse Event Reporting

### 8.1 Adverse Event Definitions

An 'adverse event' refers to any undesirable clinical occurrence in a participant, whether it is considered to be device-related or not. Adverse events (AE) may be classified as 'unanticipated adverse device effects,' 'serious adverse events,' 'significant adverse events,' or 'non-significant

Classification	Definition
Serious Adverse Event	Those events that are life-threatening, or result in permanent impairment of a body function, or permanent damage to a body structure or necessitate medical (therapeutic) or surgical intervention to preclude permanent impairment of a body function or permanent damage to a body structure.
Significant Adverse Event	Those non-serious adverse events that occur with contact lens usage that are not sight-threatening but are usually symptomatic and may warrant therapeutic management and /or temporary or permanent discontinuation of contact lens wear.
Non-Significant Adverse Events	Those less severe non-serious adverse events that occur with contact lens usage that are not sight-threatening, may or may not be symptomatic and may warrant palliative management, such as ocular lubricants or temporary interruption of contact lens wear.
Unanticipated Adverse Device Effect	Adverse events in a clinical trial that were not previously identified in the protocol in terms of nature, severity, or degree of incidence. An Unanticipated Serious Adverse Device Effect is an unanticipated adverse event that is serious in nature and caused by or associated with the device and is considered reportable.

adverse events,' as defined below.

AE classification, coding (for reporting to the sponsor) and examples are provided in the following table of Contact Lens Adverse Event Classification and Reporting table:

Code	Condition	Reporting
Serious Adverse Events		
01	Presumed infectious keratitis or infectious corneal ulcer	Notify sponsor as soon as possible, within 24 hours ; IRB reporting as per requirements
02	Permanent loss of $\geq 2$ lines of best spectacle corrected visual acuity (BSCVA)	
03	Corneal injury that results in permanent opacification within central cornea (6mm)	
04	Uveitis or Iritis (e.g. presence of anterior segment inflammation as described in ISO 11980, Annex B)	
05	Endophthalmitis	
06	Hyphema	
07	Hypopyon	
08	Neovascularization within the central 6mm of cornea	
00	Other serious event	
Significant Adverse Events		

11	Peripheral (outside central 6mm), non-progressive, non-infectious ulcer	Notify sponsor as soon as possible, within 5 working days ; IRB reporting as per requirements
12	Symptomatic corneal infiltrative event	
13	Superior epithelial arcuate lesions (SEALs) involving epithelial split	
14	Corneal staining $\geq$ dense coalescent staining up to 2mm in diameter (e.g. moderate, ISO 11980 grade 3)	
15	Corneal neovascularization $\geq$ 1.0mm vessel penetration (e.g. $\geq$ ISO 111980 Grade 2), if 2 grade change from baseline	
16	Any temporary loss of $\geq$ 2 lines BSCVA for $\geq$ 2wks	
17	Any sign and/or symptom for which subject is administered therapeutic treatment or which necessitates discontinuation of lens wear for $\geq$ 2 weeks	
10	Other significant event	

Non-significant Adverse Events		
21	Conjunctivitis (bacterial, viral or allergic)	Notify sponsor as soon as possible, within 5 working days ; IRB reporting as per requirements
22	Papillary conjunctivitis if $\geq$ mild scattered papillae/follicles approximately 1mm in diameter (e.g. ISO 11890 Grade 2), if 2 grade change from baseline	
23	Asymptomatic corneal infiltrative events	
24	Any sign and/or symptom for which temporary lens discontinuation for > 1 day is recommended (if not already classified)	
20	Other sign and/or symptom warranting classification as a non-significant adverse event	

### Normal or adaptive symptoms

Transient symptoms such as end-of-day dryness, lens awareness, itching or burning or other discomfort may occur with contact lens wear and may occasionally reduce wearing time. **These are not reported as adverse events unless in the investigator's opinion they are unexpected in nature, severe or have a high rate of occurrence.**

This clinical study will also ascertain satisfaction or preference with subjective attributes such as comfort, vision, or lens handling. Responses to these subjective questionnaires will not be considered as Adverse Events.

## 8.2 Procedures for Adverse Events

Treatment of an adverse event will depend on its nature and severity. Based on the clinical judgment of the investigator the subject may be referred to an ophthalmologist for treatment. The investigator will attempt to determine whether the reaction is related to the test device or a result of other factors. An Adverse Event Form will be completed for each adverse event. If both eyes are involved, a

separate Adverse Event Form will be completed *for each eye*. Whenever possible, the adverse event will be photo documented.

Expenses incurred for medical treatment as part of study participation will be paid by the sponsor (bills and prescription receipts kept). The subject must be followed until resolution and a written report completed indicating the subsequent treatment and resolution of the condition.

### 8.3 Reporting Adverse Events

---

All potential Serious and Unanticipated Adverse Device Effects that are related or possibly related to subject participation will be reported to the Principal Investigator and the sponsor within 24 hours of the investigator becoming aware of the event. The Principal Investigator will report the event to the IRB as soon as possible (by fax, mail/delivery, phone, or email). All fatal or life-threatening events will be reported immediately to the IRB.

Significant and Non-Significant Adverse Events will be reported to the sponsor as soon as possible, but no later than 5 working days after the occurrence.

Sponsor contact details are:

Contact:

Email:

Phone:

Address: [name]  
Suite 1  
[name]

A Data Monitoring Committee will not be necessary for this study. The Sponsor will review adverse events per SOP-526, and an impact assessment conducted if required.

### 8.4 Discontinuation from the Study

---

A subject's study participation may be discontinued at any time if, in the opinion of the sponsor or the investigator it is in the best interest of the subject. All discontinuations will be fully documented on the appropriate study forms and the Discontinuation Form will be completed.

## 8.5 Premature Study Termination or Suspension

---

The clinical study may be suspended or terminated by the Sponsor and/or the reviewing IRB at any time if, in the opinion of the Sponsor or the IRB, it is in the best interests of the study participants.

If the decision is made to terminate the study, the site will be notified to call in the study subjects, perform a final study examination, collect all of the study materials and complete study exit forms and documentation.

## 9 Device Malfunctions

---

A device malfunction means the failure of the device to meet its performance specification or otherwise perform as intended. *Any defective lens that is likely to cause or contribute to a Serious Adverse Event should be reported to the Principal Investigator and the sponsor **within 24 hours** of the investigator becoming aware of the malfunction.*

Other defective lenses should be reported to the Sponsor as soon as possible.

